#### 8.4 Procedures

The following sections describe the methods of assessments and list the type of data to be recorded in the Clinical Record Form (CRF). A detailed schedule for the different assessments is given in the flowchart in Section 3.5.6.

#### 8.4.1 EEG

EEG is measured on all patients. For this purpose the installed conventional equipment at the different sites are used. The electrodes are placed according to the standard 10-10 or 10-20 system. All standard routines in the EMUs are followed.

Data is recorded continuously throughout the entire period, where the patients are under observation (1-4 days).

#### 8.4.2 Video surveillance

All patients are under continuous video surveillance in the entire time they are under observation (1-4 days).

#### 8.4.3 ElectroCardioGraphy (ECG)

ECG is measured on all patients with the standard equipment at the sites. The standard routine in the EMU is followed.

Data is recorded continuously throughout the entire period, where the patients are under observation (1-4 days).

#### 8.4.4 EDDI

The only investigational related activities for the patients are the mounting of an EDDI.

#### 8.4.5 Overview of visits

In agreement with the established procedure the patient is firstly summoned to a talk with the physician (an investigator in the investigation) and possibly a nurse (also delegated to the investigation) regarding the purpose and the practicalities of the admission. During the talk with the physician, the patient will receive both oral and written information on the investigation.

The patient may give the written consent during the talk with the physician or during the possible talk with a nurse on the day of admission.

The clinical investigation starts at the same time as the other surveillance of the patient, in respect to the defined procedure in the EMU. In the same way the investigational part ends at the end of the admission of the patient.

#### 8.5 Monitoring plan

The Device manufacturer will initiate the participating site(s) during an on-site visit.

The progress of the clinical investigation will be monitored by the Device Manufacturer, where the focus is to verify that data accrual is happening in concordance with the protocol to ensure conclusions based on the collected data are valid and that regulatory requirements are fulfilled.

The investigator documentation will be monitored for completeness including appropriately signed informed consent forms for all included subjects. Subject identification data, inclusion and exclusion criteria, the endpoint variables and AEs will be source data verified.

At the end of the clinical investigation, all participating sites will have a close out visit.

The sponsor shall assess the extent and nature of monitoring appropriate for the clinical investigation, including the strategy for source data verification, based on considerations such as the objective, design, complexity, size, critical data points and endpoints of the clinical investigation. Results of this assessment shall be used to develop a monitoring plan.

#### 8.6 Data collection

#### 8.6.1 CRF data

The following information will be annotated in the CRF:

- Patient number
- Gender
- Age
- Diagnosis
- Monitoring, start and stop time
- For the seizures:
  - seizure type (Simple partial, complex partial, hypermotor, myoclonic, tonic, clonic, GTC, generalised – other than the above mentioned)
  - o for the GTC seizure and PNES:

- Date and time of start and stop of the seizure.
- Comments
- Investigation center
- AE type and description

#### **8.6.2 Other parameters**

- Seizure alarms recorded with EDDI (see section Error! Reference source not found.)
- EEG (see section 8.4.1)
- Video surveillance (see section 8.4.2)
- ECG (see section 8.4.3)

## 9. Statistical considerations

#### 9.1 General considerations

A one group design is chosen due to the objective of estimation of sensitivity. No hypotheses are tested, but 95% two sided confidence intervals are constructed for the measure of sensitivity and specificity.

All patients enrolled who has been wearing the device, will be included in the Full Analysis Set (FAS) which forms the basis dataset for all analyses. No subgroup analyses are planned in advance. However if the final data end up showing equally distributed amounts of seizures from both kids and adults, we may study the result in the two subgroups.

The primary endpoint, the sensitivity, will be calculated as described in section 3.5.1 along with a 95% confidence interval (CI). The expectations for sensitivity (true positive assessments) are a lower limit of the two-sided 95% CI of more than  $95\% \pm 5\%$ .

The specificity is calculated and evaluate indirectly as the false detection rate (the number of false detections per hour). This parameter will be estimated along with 95% CI.

The effect of the GTC seizure alarm in a nocturnal situation (23:00 - 07:00) is found. Both the sensitivity and specificity will be calculated based on the data within this period of time (23:00 - 07:00) for each day and analyzed similarly to the analysis of the 24h periods.

Each false alarm is evaluated based on the video data to figure out, what may have caused it.

Adverse events (AEs) are summarized descriptively by type. Please refer to section 16 for details on AE collection types.

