#### 3.2 Purpose

The purpose of this clinical investigation is to test the reliability of the epileptic GTC seizure detection device EDDI. Furthermore the study should also evaluate whether the device is able to differentiate the convulsive epileptic (GTC) seizures from non-epileptic convulsive seizures.

EDDI will be tested on patients with epilepsy, who are expected to experience GTC seizures (or nonepileptic psychogenic seizures) during their admission to one of the epilepsy monitoring units (EMUs) participating in the study. These (patients with epileptic GTC seizures) constitute the patient group for which EDDI is intended.

In the investigation the only change from a normal admission in the EMU is the addition of the EDDI, which is placed on the outer side on one of the upper arms of the patient, as shown in the Instruction For Use (IFU) of the device.

It is validated, that this addition will not add any risks to the participating patients.

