## 3.5.2 Secondary endpoints

- The specificity is calculated and evaluated indirectly as the false detection rate (the number of false detections per hour). A detection is categorized as a false detection, if it falls outside a seizure period (between start and end of a seizure, defined by the gold standard). Possible alarms during placement or removal of the device are discarded (this will only happen if the device is used wrong). All data (incl. video and EEG) are saved for each patient, which makes it possible to find the reasons for possible false alarms.
- Effect of the GTC seizure alarm in a nocturnal situation (23:00 07:00). The sensitivity will be calculated based on the data within this period of time (23:000 07:00) for each day.
- The nocturnal specificity will be calculated as the amount of false positives within the nocturnal period (23:00 07:00) for all days, with respect to the amount of hours.
- For each possible false alarm, the reason for it is checked to see if there is a reasonable explanation.
- The measure for whether the EDDI captures the PNES is calculated as the total number of PNES minus the number of captured PNES and divided by the total number of PNES. This means that a measure close to 100% ensures that the device will not alarm on PNES, and the closer the measure is to 0%, the more false alarms may come from PNES.

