## 8. Design of the clinical investigation

#### 8.1 General

The investigation is designed as an assessor controlled double-blinded clinical investigation assessing the sensitivity and specificity of EDDI, in detection of GTC seizures in epileptic patients. As a secondary outcome the study furthermore tests EDDI's ability NOT to alarm on PNES.

The assessor is a physician at the site(s) and will provide details on seizure type and time, based upon the gold standard: video monitoring and EEG. The EDDI will not provide a visual or audible indication whether an alarm has occurred. In this way, the assessor will remain blinded to the alarms set by EDDI. The EDDI works in real time and will thereby be blinded from the annotations by the clinical personnel.

The seizure times obtained by the EDDI will be transferred to a computer. This data has an audit trail and cannot be changed.

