#### 9.2 Sample size consideration for alarm correctness

With an expected sensitivity of 95%, a sample size of at least 19 patients with epileptic GTC seizures is needed. Based on this it has been chosen to include 20 patients with epileptic GTC seizures and furthermore 10 patients with PNES. To succeed in this inclusion, it is expected that about 80 patients will be included in total.

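### The false detection rate is defined on all device wearers, who can include patients with PNES and no epilepsy, although the protocol says specificity is assessed in patients with epilepsy

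*Protocol*

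**What the plan says.** **Population in which specificity is assessed.** Protocol section 8.1 describes the investigation as "assessing the sensitivity and specificity of EDDI, in detection of GTC seizures in epileptic patients", and section 3.3 says the same of patients with epilepsy. Section 3.2 adds: "These (patients with epileptic GTC seizures) constitute the patient group for which EDDI is intended".

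**How specificity is measured.** Section 9.1: "The specificity is calculated and evaluate indirectly as the false detection rate (the number of false detections per hour", followed by "This parameter will be estimated along with 95% CI". The nocturnal rate is to be analysed in the same way. Section 3.5.2 gives the counting rule: "A detection is categorized as a false detection, if it falls outside a seizure period".

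**Analysis set.** In section 9.1, enrolled patients who wore the device "will be included in the Full Analysis Set (FAS) which forms the basis dataset for all analyses". The section continues: "No subgroup analyses are planned in advance". The only split it contemplates is children versus adults, and that is conditional. Section 8.3 instead limits the final evaluation to patients with GTC seizures or PNES.

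**Who can enter.** Inclusion criterion 2 (section 3.5.3.1) accepts a history suggesting either an epileptic or a non-epileptic convulsive event. Section 9.2 plans 20 patients with GTC seizures and "furthermore 10 patients with PNES" among about 80 enrolled. Section 3.3 gives both targets as approximate and the total as 70 to 80.

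**The concern.** Nothing in the definition of the false detection rate restricts it to patients with epilepsy, and neither of the two analysis sets does so. A patient with PNES and no epilepsy contributes monitored hours to the denominator and any false alarms to the numerator. How many such patients there are depends partly on a recruitment target, not on how often such people would use the device.

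Sensitivity is not touched, because it is counted over GTC seizures only. The false detection rate stands beside it as the main measure of reliability, and its stated target is patients with epilepsy. If PNES-only patients alarm more or less often per hour, the reported rate shifts with their share of the hours. A reader of the planned summary would not see by how much.

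**Working it through.** **The plan's own figures.** The protocol derives no number for the false detection rate. Its only derived figure is the minimum of 19 GTC patients in section 9.2. That reproduces as 1.96² × 0.95 × 0.05 / 0.10² = 18.25, rounded up to 19, with a half-width of 10 points that is inferred and not stated. It concerns sensitivity and does not bear on this point.

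**Formula.** Let *w* be the share of monitored hours from patients with PNES and no epilepsy, and *m* their false detection rate divided by that of epilepsy patients. Then

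combined rate / epilepsy rate = (1 − *w*) + *w* × *m*.

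**Inputs.**
- PNES target 10, GTC target 20, total about 80 (sections 3.3, 8.3 and 9.2).
- Assumed: all 10 PNES patients have no epilepsy, nobody else lacks it, and mean wear time is equal.
- *w* in the full analysis set: 10/80 = 12.5% (10/70 = 14.3% with 70 enrolled).
- *w* in the section 8.3 set: 10/30 = 33.3%.
- *m*: not given in the protocol, so assumed to lie between 0.5 and 2.

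**Results (combined rate / epilepsy rate).**

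| Set | *m* = 0.5 | *m* = 1 | *m* = 2 |
|---|---|---|---|
| Full analysis set, *w* = 12.5% | 0.875 + 0.0625 = 0.94 | 1.00 | 0.875 + 0.25 = 1.13 |
| Section 8.3 set, *w* = 33.3% | 0.667 + 0.167 = 0.83 | 1.00 | 0.667 + 0.667 = 1.33 |

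With 70 enrolled, the full-analysis-set range is 0.93 to 1.14.

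**Scale.** Section 2.1 cites 0.04 per hour from the second study. If that were the epilepsy rate, the combined rate would be 0.0375 to 0.045 per hour in the full analysis set (0.04 × 0.9375 and 0.04 × 1.125). In the section 8.3 set it would be 0.033 to 0.053 per hour.

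**Uncertainty in *w*.** Some PNES patients may also have epilepsy, which lowers *w*, to zero if all of them do. Some of the remaining 50 or so patients (80 − 30) may prove not to have epilepsy, which raises it in the full analysis set.

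**Uncertainty in *m*.** The counting rule in section 3.5.2 refers to a seizure period without saying GTC. Section 8.6.1 records start and stop times for GTC seizures and PNES alike, and section 10.1 calls the PNES events seizures. Read that way, an alarm during a PNES event is not a false detection. The last item of section 3.5.2, however, treats alarms on PNES as false alarms. The choice between these readings affects *m*.

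**The case against.** The best case against runs as follows. The specificity objective in section 7.1.2 speaks of avoiding false alarms and names no population. Telling GTC seizures from non-epileptic ones is part of the purpose in section 3.2, and that section loosely describes everyone tested as a patient with epilepsy. PNES has its own endpoint, and each false alarm is reviewed for its cause. Diagnosis and monitoring times are in the CRF. Tables by diagnosis are detail that an SAP often supplies.

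Much of this limits the point, and four stronger readings that a reader might infer are not supported:

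- *That a fixed PNES quota sets the weight.* Section 3.3 says approximately 10, no cap is stated, and the mix also depends on referrals.
- *That the rate is known to be inflated or diluted.* The protocol gives no value for *m*. Section 10.1 expects no PNES events to be detected, which would make dilution plausible, but that says nothing about alarms outside those events.
- *That the rate in epilepsy patients is lost.* It can be computed from the planned CRF data; it is only not planned as a result.
- *That an epilepsy-only rate would match the intended users or the sensitivity population.* Epilepsy patients without GTC seizures would still be in it.

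The mismatch itself remains. The PNES endpoint is the share of PNES events without an alarm, and it leaves those patients' hours in the rate. The inclusion criteria do not require epilepsy. On subgroups the protocol is not silent: it names one set for all analyses and disclaims planned subgroups.

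**Conclusion.** The point holds as a mismatch between the stated population and the defined rate. Sections 3.3 and 8.1 promise specificity in patients with epilepsy, while sections 3.5.2 and 9.1, or section 8.3, define a rate that can include patients without it.

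The numerical effect is conditional. It is zero if the rates are equal or if no PNES-only patients are enrolled. Otherwise it is modest in the full analysis set and larger in the section 8.3 set, with unknown direction. The ranges in the working rest on 10 PNES-only patients, equal wear time and an assumed rate ratio of 0.5 to 2; none of these is fixed by the protocol. The point is worth correcting because the correction is cheap and is more convincing when stated in advance.

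**What to change.** In sections 3.5.2 and 9.1, state in substance:

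*The false detection rate (24 h and nocturnal), with its 95% CI, is reported first for patients with a diagnosis of epilepsy, with those who had GTC seizures also shown. It is then reported separately for patients with PNES only and for patients with an undetermined diagnosis. The rate over the full analysis set is given as a supplement. Diagnosis is taken from the CRF and assigned without knowledge of the device alarms.*

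In the same edit:
- say whether a detection during a PNES event counts as a false detection;
- reconcile the evaluation set of section 8.3 with the full analysis set of section 9.1.

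**Cost.** Some wording and a few table rows; Diagnosis and monitoring times are already collected (section 8.6.1). The headline interval widens somewhat. If only 10 of 80 patients leave it and the rate is unchanged, the width grows by about 1/√0.875 = 1.07 on a normal approximation. With no false alarms at all, the upper limit rises by 1/0.875 = 1.14. The widening is greater if patients with an undetermined diagnosis also leave.

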#### 9.2 Sample size consideration for alarm correctness

With an expected sensitivity of 95%, a sample size of at least 19 patients with epileptic GTC seizures is needed. Based on this it has been chosen to include 20 patients with epileptic GTC seizures and furthermore 10 patients with PNES. To succeed in this inclusion, it is expected that about 80 patients will be included in total.

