## 2. General

## 2.1 Introduction

Epilepsy is the second most common acute neurological disorder, with a world-wide prevalence of 0.8-1.0% [1]. A third of the patients are medically refractory [2-4], and where no other treatment (surgery, ketogenic diet) has an effect, an automatic detection alarm would be of great help to the patients and their relatives.

In a quantitative study we found biomarkers for the differences of epileptic and physiologic tonic activity [5]. Based on the findings a generalized tonic-clonic (GTC) seizure detection algorithm was designed based on conventional surface ElectroMyoGraphy (surface EMG / sEMG), which proved to work with a sensitivity of 100% and a false detection rate (FDR) of 0.04/h in a second study [6]. In a third study this algorithm was implemented into a wireless sEMG device (IctalCare Research Investigation System (IRIS)) and tested on patients. It proved to show equally well results for the sensitivity, and the FDR was decreased to 0/h [7].

A second generation of the wireless sEMG device (EDDI) is designed and this clinical study will serve as a confirmative study, to prove the reliability (based on sensitivity and FDR) of the product.

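### The 19–20 GTC patients in 9.2 correspond to about ±10 points of precision and do not support the lower confidence limit expected in 9.1, which is itself not a single threshold

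*Protocol*

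**What the plan says.** Section 9.2 gives the whole sample size argument in one sentence: "With an expected sensitivity of 95%, a sample size of at least 19 patients with epileptic GTC seizures is needed". It then says that "it has been chosen to include 20 patients with epileptic GTC seizures and furthermore 10 patients with PNES". It states no half-width, no interval method and no expected number of seizures per patient.

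Section 9.1 describes an estimation study: "No hypotheses are tested, but 95% two sided confidence intervals are constructed for the measure of sensitivity and specificity". It nevertheless sets a numerical expectation for the primary endpoint: "The expectations for sensitivity (true positive assessments) are a lower limit of the two-sided 95% CI of more than" 95% ± 5%.

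Section 3.5.1 defines sensitivity as the number of GTC seizures detected divided by all GTC seizures on the gold standard. The endpoint therefore counts seizures, while 9.2 counts patients. Sections 3.3 and 8.3 limit participation to 4 days. Section 2.1 says that "this clinical study will serve as a confirmative study, to prove the reliability" of the product.

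**The concern.** A sample size statement and an expected lower limit for the same endpoint should follow from each other. Here the only margin printed is 5 points, and 19 patients is far too few for that margin. The expectation also has no single value: a lower limit of 92% would meet one reading and miss the other, so the choice could be made after the data are seen.

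Section 2.1 presents the study as confirmatory. If every one of 20 patients had one seizure and all were detected, the data would support a lower limit of about 83%, not 90% or 95%. A reader of 9.1 and 9.2 together would expect more than that.

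**Working it through.** **Inputs.** Expected sensitivity 95% and 19 (planned 20) GTC patients, from 9.2. Two-sided 95% intervals and the expression 95% ± 5%, from 9.1. Seizures as the unit of the endpoint, from 3.5.1.

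**Step 1: reproduce the 19.** The normal-approximation size for half-width d is n = 1.96² × p(1 − p) / d².

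- d = 0.10: 3.8415 × 0.0475 / 0.01 = 18.2, rounded up to 19. This matches.
- d = 0.05: 3.8415 × 0.0475 / 0.0025 = 72.99, rounded up to 73.

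The half-width at p = 0.95 is 1.96 × √(0.0475/n), which is 9.8 points for n = 19 and 9.6 points for n = 20. A symmetric interval of 95% ± 9.6 points would pass 100%, so the approximation is poor at this size.

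**Step 2: lower limit with one observation per patient.** With no misses, the exact (Clopper-Pearson) lower limit is 0.025^(1/n).

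| Two-sided 95% lower limit | 20/20 | 19/20 |
|---|---|---|
| Exact | 83.2% | 75.1% |
| Wilson | 83.9% | 76.4% |
| Agresti-Coull | 81.0% | 74.6% |
| Jeffreys | 88.3% | 78.9% |
| Wald | 100% (zero width) | 85.4% |

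Except for the zero-width Wald interval at 20/20, every value is below 90%, the more lenient reading.

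**Step 3: lower limit in the endpoint's own unit.** Treat seizures as independent and use the exact interval.

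- Above 90%: at least 36 seizures with no misses (0.025^(1/36) = 90.3%), 54 with one miss, or 70 with two. Across 20 patients, 36 is 1.8 seizures each and 54 is 2.7.
- Above 95%: at least 72 with no misses (0.025^(1/72) = 95.0%), or 3.6 per patient.

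**Step 4: chance of getting there if true sensitivity is 95%.**

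- 36 independent seizures, where none may be missed: 0.95^36 = 15.8%.
- 73 independent seizures, where at most two may be missed: 28.7%.
- A limit above 95%: about 2.5% of trials or fewer, because a valid two-sided 95% interval lies wholly above the true value that rarely. For example, 0.95^72 = 2.5%.

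**Step 5: direction of the clustering effect.** Seizures in one patient share the same muscle, electrode position and seizure pattern, so they are unlikely to be independent. As an illustration with an assumed equal number per patient, 36 seizures in 20 patients have a design effect of 1 + 0.8ρ. For an assumed correlation ρ of 0.1, 0.3 and 0.5, the effective number is 36/1.08 = 33, 36/1.24 = 29 and 36/1.40 = 26. The documents give no value of ρ. Any positive value raises the counts in step 3.

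**The case against.** The strongest reply concerns the unit. Sensitivity is a proportion of seizures, so 20 patients do not mean n = 20. A reader might infer from step 2 that the expectation in 9.1 could not be met even with perfect detection. The protocol does not support that: 36 or more seizures with none missed would give an exact limit above 90% if clustering is ignored, and nothing excludes 1.8 seizures per patient. Equally, nothing in the protocol assumes it, and 9.2 does not make this argument. The reply removes the absolute claim but shows that the size is stated in the wrong unit.

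Second, ±10 points is inferred. A one-sample normal-approximation test of 95% against 70%, with two-sided 5% and 80% power, also gives 19: ((1.96 × √0.21 + 0.842 × √0.0475) / 0.25)² = 18.7. This is the less likely source, because 9.1 says "No hypotheses are tested", and it does not support a 90% limit either.

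Third, 9.1 speaks of expectations. A reader might take the limit as a pass/fail criterion on which the trial succeeds or fails. No decision rule is tied to it, so that reading goes too far. It remains the one numerical benchmark that 9.1 sets for the lower limit of the primary endpoint.

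Fourth, the choice of interval method may properly sit in a statistical analysis plan. That is fair, and its absence is not the point here. No usual method makes 19 or 20 observations give ±5 points at 95%.

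Finally, one might say that an expected 95% can never give a lower limit above 95%. That holds for an observed 95%. If 95% is the true value, such a limit is possible but rare (step 4).

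**Conclusion.** The point holds: two figures in the protocol conflict. The 19 patients in 9.2 match a half-width of about ±10 points at 95% sensitivity, whereas ±5 points would need 73 independent observations. The expectation in 9.1 can mean 90% or 95%. On the patient count that 9.2 uses, the exact lower limit is 83.2% at best and 75.1% with one miss, below both.

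Counted in seizures, a limit above 90% is possible but neither planned for nor likely at the protocol's own assumed sensitivity: about 16% with 36 independent seizures and 29% with 73. A limit above 95% is very unlikely in any unit. These probabilities assume independent seizures, a true sensitivity of 95% and the exact interval. A higher true sensitivity would raise them, and within-patient correlation would raise the number of seizures needed.

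**What to change.** No extra patients are needed. The change is a short amendment to two sections.

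- **Section 9.2.** State that 19–20 patients correspond to about ±10 points at 95% sensitivity if each contributes one observation, and that ±5 points would need 73 independent observations. Then express the size in the endpoint's unit: give an assumed number of GTC seizures across the 20 patients and the lower limit that follows with none and with one missed. The per-patient limits of 83% and 75% should not be presented as the expected result unless one seizure per patient is the stated assumption.
- **Section 9.1.** Remove 95% ± 5%. Either keep pure estimation, consistent with the statement that no hypotheses are tested, or give one threshold that the planned size can reach.
- **Interval.** Here or in the statistical analysis plan, use a method that stays valid near 100% (exact or Wilson rather than Wald) and that allows for several seizures from one patient.

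The cost is that the stated precision becomes less favourable, and the sponsor must commit to an assumption about seizure numbers that the protocol now leaves open.
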